## **5.2 Recruitment Methods**

**Aim 1:** We will recruit participants through MH RRTPs at each site. Veterans entering these programs will be screened by MH RRTP staff in consecutive order during the admissions process to determine study eligibility. Specifically, during the admissions process into the MH RRTP, a staff member will ask the Veteran if they were arrested and charged with a criminal offense and/or released from incarceration in the past 5 years. This is a standard question of all Veterans who enter MH RRTPs at each site. In addition, the MH RRTP staff member will verify that the Veteran is not pregnant and is conversant in English. MH RRTP staff will then ask eligible patients for permission to be contacted about the study by project staff (i.e., the MH RRTP staff member will hand the Veteran the Recruitment Sheet) and will provide study personnel with a list of these patients and their contact information (i.e., their phone number) three times per week. If the number of patients referred to the study exceeds recruitment goals, we will randomly select as many patients as needed. At each site, we will keep a list of all eligible patients whom we contacted to solicit participation in the study. Prior to contacting a potential patient, we will first verify that that patient was not already approached about participating in the study during a previous admission.

We plan to enroll approximately five patients per month at each site (approximately 1-2 patients per week). This approach aligns with standard delivery of MRT, which consists of open groups with rolling enrollment. The proposed pace will maintain appropriate group size for the MRT group facilitator and allow the research assistants to conduct assessments. 365 patients will be enrolled and complete baseline interviews. The sample will be stratified by site such that 122 patients (with rounding) will be recruited separately from Palo Alto, Little Rock, and Bedford, with 61 patients entering into each condition at each site. Regardless of group assignment, participants will also be asked to complete an in-person baseline assessment and two follow-up assessments (in-person or via phone) 6 and 12 months later. Participants will be reimbursed \$25 for the baseline interview, and \$50 after completion of each follow-up interview. Participants will have the option of being reimbursed with gift cards immediately after the completion of each interview, or receiving a check via mail in 6-8 weeks.

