## 5.6 Data Analysis

**Sampling plan: Power analysis.** To ensure sufficient variability in our outcomes, and in turn increase the power to test study hypotheses, we focused our Specific Aims on overall risk for recidivism (i.e., PICTS GCT total scores) and functioning on health-related risk factors, rather than recidivism per se (e.g., rearrest), as the latter may have a low base rate within the 12-month study period. Based on meta-analyses and studies of MRT mechanisms, we expect a medium effect size (Cohen's  $f^2=.15$ ) in multiple regression models testing condition (UC vs. MRT) as a predictor of recidivism risk and the health-related outcomes. However, given the planned moderation analyses, we calculated the power to detect small effect sizes (i.e.,  $f^2=.02$ ). To account for having patients at three sites, power analyses using G\*Power were based on having six cells (two conditions per site). A sample size of 292 (146 in each condition) will provide 80% power to detect a small effect size at an alpha of .05 (two-tailed test). To account for the moderators, we calculated the available power and effect size that could be detected in a regression model, given (a) our projected sample size, and (b) the addition of six more predictors in the model (i.e., the three moderator variables listed above and three interaction terms between these moderators and the variable of condition). Based on an N of 292 and alpha of .05, we would have 80% power to detect an  $f^2$  of .07, a small-to-

medium size effect. We are predicting 20% attrition at the follow-ups. This was the rate of attrition in prior longitudinal studies of project team members of Veteran treatment samples with high rates of criminal histories. Thus, we will recruit a total of 365 patients (183 in each condition, with rounding). If attrition reaches 30%, we will still have 80% power to detect an  $f^2$  of .08.

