Examine mechanisms (i.e., reasons MRT is effective). MH RRTP completion (yes/no) and SUD/mental health continuing care utilization (outpatient attendance [yes/no] and amount; mutual-help group attendance [yes/no], number of meetings) will be examined as mediators between condition and risk for recidivism, and between condition and the health-related outcomes at the 6- and 12-month follow-ups. We will conduct regression models that correspond to a hypothesized causal sequence among (1) MRT, (2) one of our hypothesized mediators, and (3) better outcomes. In each model, we will control for relevant covariates (e.g., baseline values for sociodemographics and the dependent variable). In the first regression, a dummy variable representing the MRT intervention will be the independent variable and the dependent variable will be the outcome (e.g., PICTS GCT scores). In the second regression, MRT will be the independent variable and the dependent variable will be the potential mediator. In the third regression, the potential mediator will be the independent variable and the dependent variable will be the outcome. If the coefficient for MRT or a potential mediator is significant in all of these cases, we will proceed. In the final regression, the MRT dummy variable will be entered simultaneously with the potential mediator as predictors of the outcome. If the coefficient for the potential mediator is significant and the coefficient for the MRT dummy variable on the outcome is reduced, we will conclude that mediation is supported and will evaluate whether the indirect effect is significant. To account for variability in intensity of continuing care services, we will test for significant interactions on outcomes between our measures of continuing care and a variable for site.

We will also determine if any significant, direct effects of MRT on (a) overall risk for recidivism, and (b) the health-related outcomes, are mediated by specific mechanisms of MRT (i.e., improvements in interpersonal functioning and reductions in affiliations with antisocial and substance abusing peers). We will conduct GLMM regression models that correspond to a hypothesized causal sequence among (1) MRT (vs. UC), (2) the potential mechanisms, and (3) one of the outcomes, and control for covariates. Finally, we will conduct regression analyses

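### The care-by-site interaction test does not adjust for sites delivering different amounts of continuing care, and the regressions that decide mediation (hypothesis 1c) name no site term

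*Combined protocol and SAP*

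**What the plan says.** Section 5.6, under the mechanisms heading, tests programme completion and continuing-care use as mediators through four regressions: outcome on MRT, mediator on MRT, outcome on mediator, and outcome on MRT and mediator together. If the coefficients of the first three are significant, the fourth is fitted. Mediation is supported if the mediator is significant there and the MRT coefficient shrinks; the indirect effect is then tested.

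On covariates the plan says "In each model, we will control for relevant covariates (e.g., baseline values for sociodemographics and the dependent variable"; the list is introduced by e.g. and does not mention site.

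Site enters this part of the plan once: "To account for variability in intensity of continuing care services, we will test for significant interactions on outcomes between our measures of continuing care", where the other term of each interaction is site. Intensity is not defined, and nothing says what follows a significant or a non-significant result.

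Section 5.5 measures care as received or not, and as counts of outpatient visits and mutual-help meetings. Section 5.2 makes site a stratum: "The sample will be stratified by site such that 122 patients (with rounding) will be recruited separately" at each of the three, "with 61 patients entering into each condition at each site". The condition-by-site interaction in section 5.6 belongs to the model comparing arms on outcomes, not to the mediation regressions.

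**The concern.** The sponsor evidently expects continuing care to vary by site. With care recorded as yes/no and as counts, one obvious form of that variation is that some sites deliver more of it. More care at a site shifts the level of the mediator there. It does not change how much the outcome moves per visit, and only the latter is tested by a care-by-site interaction.

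Balanced allocation within site protects the path from MRT to care. It does not protect the path from care to outcome, because the amount of care a patient receives is not randomised. If a site has both more care and better outcomes for unrelated reasons, a regression without site mixes the between-site association into the care coefficient.

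At stake is hypothesis 1c: an indirect effect could be credited to continuing care when the care coefficient reflects which site the patient attended. Site differences running in the opposite direction could hide real mediation.

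**Working it through.** **Inputs from the documents.** Two-sided alpha .05 and "A sample size of 292 (146 in each condition) will provide 80% power" (section 5.6). "We are predicting 20% attrition at the follow-ups", and 292 / (1 − 0.20) = 365, which reproduces the recruitment target. Three sites, 1:1 within site (section 5.2). The simulations use 3 × 97 = 291 patients. The plan attaches no figure to the mediation analysis, so there is none to reproduce.

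**Assumed inputs.** Care and outcome are standardised within site. Site means are −d, 0, +d, with d_m for care and d_y for outcome. MRT raises care by 0.3 SD and shifts the outcome by 0.28 SD. The true effect of care on outcome is zero.

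**Step 1: what the interaction test sees.** Its null hypothesis is an equal care-outcome slope at every site.
- Sites differ only in amount of care, or in amount and outcome level: the 2-df test rejects in 4.3% to 6.2% of runs, its nominal level. Comparing mean care across sites directly rejects in about 89% (steps of 0.25 SD between adjacent sites) to 100% (0.5 SD or more).
- Sites differ in effect per unit of care (slopes −0.6/−0.3/0, or −0.5/−0.3/−0.1): it rejects in 97% and 71%.

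**Step 2: bias in the care coefficient without site.** The variance of the three site means is (2/3)d², so the expected coefficient is

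b = (2/3)·d_m·d_y / [1 + (2/3)·d_m²].

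- d_m = 0.5, d_y = 0.2: b = 0.0667 / 1.1667 = 0.057. Residual variance is 1 + 0.0267 − 0.057² × 1.1667 = 1.023. SE = √[1.023 / (291 × 1.1667)] = 0.055, so z = 1.04. The rejection rate is P(Z > 0.92) + P(Z < −3.00) = 18%.
- d_m = 0.8, d_y = 0.3: b = 0.16 / 1.4267 = 0.112, SE = 0.050, z = 2.24, rejection rate 61%.

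**Step 3: add the baseline outcome, as the plan states.** Assume a baseline-to-follow-up correlation of 0.6 and site differences in outcome already present at baseline. The numerator is multiplied by 1 − 0.6 = 0.4, and the denominator becomes [1 + (2/3)d_m²][1 + (2/3)d_y²] − [(2/3)d_m·d_y]².
- First scenario: b = 0.0267 / 1.193 = 0.022.
- Second scenario: b = 0.064 / 1.487 = 0.043.

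**Step 4: simulated rates** (3,000 to 4,000 trials per scenario in most runs). The full sequence means all four regressions pass.

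| Site spread in SD (care, outcome) | Quantity | No baseline, no site | Baseline, no site | Site included |
|---|---|---|---|---|
| ±0.5, ±0.2 | Care coefficient, final regression | 18% | 7–8% | about 5% |
| ±0.5, ±0.2 | Full sequence | 7–8% | 3–4% | about 1% |
| ±0.8, ±0.3 | Care coefficient, final regression | 60% | 18–19% | about 5% |
| ±0.8, ±0.3 | Full sequence | 22–23% | 9% | about 1% |

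A Sobel test of the indirect effect (an assumed choice) passes in 2.1% and 8.7% of trials without baseline, and 0.9% and 1.8% with it.

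**Step 5: limits of the effect.**
- Small spreads (care ±0.3, outcome ±0.1): coefficient significant in 6% to 6.5% without baseline, close to nominal.
- Sites differ in care only: no inflation.
- No MRT effect on care: false mediation after the Sobel test is at most 0.4%.
- MRT effects of 0.5 SD on both care and outcome, first scenario, no baseline: full sequence 17%, against about 2% with site.
- Site steps of 0.5 SD in both care and outcome, with the same 0.5 SD MRT effects and no baseline: 51% after the Sobel test, against 1.3% with site.

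**The case against.** Five arguments can be made for the plan.

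1. **Intensity may mean what a visit delivers.** The number of visits is already the mediator, so variability in intensity can naturally mean effect per visit. The interaction is then the right test, and step 1 shows that it works. This stands: a reader might infer that the test cannot detect intensity differences at all, and the documents do not support that, because the term is undefined. Differences in amount remain unaddressed.

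2. **Site is unnamed, not excluded.** The covariate list is open, and a model with a care-by-site interaction would normally carry a site main effect. This also stands. However, the moderator paragraph of section 5.6 says explicitly that main effects enter with their interactions, and nothing similar is said for site here. A site main effect in the interaction model would still not put site into the third and final regressions.

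3. **The baseline outcome is a planned covariate and the decision has several steps.** A reader might take 18% or 60% as the rate of false mediation claims. They are not: they count one coefficient, without the baseline outcome. The baseline-adjusted, full-sequence figures are much lower. That protection depends on site differences being present at baseline and is lost if they arise afterwards.

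4. **The plan does not say a non-significant interaction would be used to drop site.** Correct; that is a possible use of the result, not a stated one.

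5. **Site is only one confounder of a non-randomised mediator.** True, and adding it would not make the path causal. It is nonetheless a recorded stratum that the sponsor already regards as relevant to care.

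**Conclusion.** The concern holds in a limited form. The interaction test detects a different effect per unit of care across sites. It does not detect or adjust for different amounts of care, and no site term is named in the regressions that decide hypothesis 1c.

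False mediation from this source needs three things together: sites differing in amount of care, sites differing in outcome, and MRT affecting care. The third is what hypothesis 1c predicts; the documents give no figures for the first two. Under the assumed moderate spread and the planned baseline adjustment, the inflation is modest: about 7 to 8% against 5% for the coefficient, and 3 to 4% against about 1% for the full sequence. Under the larger spread it is material: 18 to 19% and 9%. With small site differences it is negligible.

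A reader might extend this to the arm comparisons in 1a and 1b. The documents do not support that, since allocation is balanced within site.

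**What to change.** In the mechanisms part of section 5.6, replace the sentence on care-by-site interactions with wording to this effect: all mediation regressions include site as a fixed effect (two indicators) alongside the baseline value of the outcome, so that the mediator coefficient is a within-site association; care-by-site interactions are an exploratory check of whether the effect per unit of care differs by site, reported as site-specific slopes with 95% confidence intervals; a non-significant interaction does not justify omitting site. Define intensity in the same place, as amount of care, effect per unit of care, or both.

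The cost is a change of wording and two degrees of freedom out of about 290. Site is already recorded as the recruitment stratum, so no further data are needed.

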UC condition. All patients, regardless of condition, will receive usual MH RRTP care at the Palo Alto, Little Rock, and Bedford VAs. At each site, we will recruit from residential treatment programs that serve veterans dealing with homelessness, substance abuse, and/or mental health issues. These MH RRTPs aim to improve Veterans’ health and facilitate community reintegration by providing care (24 hours per day, 7 days per week) using a structured residential environment. The participants’ health care providers at the MH RRTPs (not the study team) will be providing usual care. No standard treatment will be withheld.

MRT condition. Patients assigned to the MRT condition will receive usual care in the MH RRTP plus two hours of MRT weekly, which will begin within a week of entering the MH RRTP in order to complete all sessions during the 3-month program stay. Over the course of 12 weeks, they will attend 24 group sessions (one-hour sessions, twice per week). The overall length of the intervention (12 weeks) corresponds to the national average of bed days of care for Veterans in MH RRTPs (3 months). In FY13, an average of 70% of patients entering the MH RRTPs at the Palo Alto, Little Rock, and Bedford VAs stayed at least 90 days (approximately 13 weeks). Thus, the majority of patients will have full exposure to the 12-week intervention by virtue of staying in the MH RRTP. For the patients who do not stay for 12 weeks, continuing care services are still available at the MH RRTP at each site, and those who have not yet completed the full MRT protocol when they discharge from the MH RRTP will still be able to get full exposure to the intervention as outpatients, and will be encouraged to do so.

The MRT curriculum consists of short assignments, grounded in cognitive-behavioral techniques, which move participants through 12 steps that aim to restructure antisocial cognitions and behaviors. To progress through the steps, patients complete homework between group meetings and at the next group each patient presents his/her homework to the group members for feedback. Participants move through steps at a rate of approximately 1-2 sessions and group sessions can incorporate new members at any time. With open enrollment, patients are presenting on different steps, which is advantageous because those who have progressed farther are able to share their insights to newer patients who are at lower steps. Open

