enrollment is also advantageous as it allows for recruitment of all eligible patients as they enter the MH RRTPs.

The MRT groups will be facilitated by a combination of (a) members of the research team who are already listed in this application, (b) to-be-named (TBN) VJP Specialists from the local facility who are not MH RRTP staff, and (c) TBN staff members of the MH RRTP at each site. To reduce risk of contamination, the TBN staff members from the MH RRTPs will be specifically instructed to not provide the study intervention to any Veterans who were assigned to the usual care condition.

A full dose of MRT is 24 sessions over 12 weeks. To facilitate patients' completion of the full dose, we will (a) remind patients at the end of each MRT session about the treatment schedule and emphasize the importance of full participation; (b) contact patients who miss a session to determine the reasons for the absence and encourage participation in future sessions; (c) offer incentives (e.g., certificates) to patients who complete the full dose – such incentives are highly valued by Veterans as it allows them to demonstrate to court-related decision makers that they complied with treatment; (d) encourage participation in MRT groups as outpatients for those who have not yet completed the full dose when they discharge from the MH RRTP. These efforts notwithstanding, there is evidence that smaller doses of MRT can be effective (i.e., completion of seven steps in the MRT curriculum can lead to long-term positive changes). According to [name] and VJP Specialists who have run MRT groups, a minimum dose for this study is 12 sessions. To maximize clinical usefulness of the data, we will also examine outcomes as a function of dose.

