(controlling for relevant covariates) to examine associations of MRT dose (number of group sessions attended; number of steps completed) with patient outcomes at the follow-ups. Based on prior work and the recommendations of VJP Specialists who have previously conducted MRT groups with Veterans, we will explore whether completion of 12 sessions is as effective as a full dose (24 sessions).

Adjust for contamination and missing data. To address the possibility of contamination, if we learn that MRT-related information was shared with UC participants, the records of those UC participants will be flagged, and contamination-adjusted intention-to-treat analyses will be calculated (i.e., the effect of treatment assignment on outcomes is adjusted by the percentage of participants assigned to the UC condition who may have received the treatment). To minimize missing data, we will train research assistants on the importance of completing each item while respecting the rights of patients to refuse answers. Based on our prior studies, we expect to achieve less than 5% missing data on each variable at each assessment, over and above any attrition. We will obtain as high a follow-up rate as possible at each assessment. In contrast to MH RRTP completion and SUD/mental health continuing care utilization, which will be collected primarily via VA administrative data at the 6- and 12-month follow-ups, data on recidivism risk and health-related outcomes at the follow-ups will be collected via patient reports, and will therefore have more missing data due to expected attrition at those time points. GLMM's strengths are the ability to use all available data, including data on respondents who may not have provided data at each assessment. All patients who enter the study will be included in GLMM analyses. However, we will also conduct analyses that include only patients who attended at least the first MRT session. We will use a model-based multiple imputation procedure and will impute missing values using least-squares regression imputation. We will select a set of measures that are associated with the variable at issue and use it in a series of iterated least-squares regression models to generate a predicted value for the variable being imputed, and then substitute the missing value with the predicted value.

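### The exploratory 12-versus-24-session comparison asks an equivalence question of non-randomised attendance, with no margin and no limit on when sessions count, so a null result cannot support equal effectiveness

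*Combined protocol and SAP*

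**What the plan says.** The dose analysis is specified in two sentences at the end of the mechanisms part of section 5.6. It opens with "Finally, we will conduct regression analyses", qualified by "controlling for relevant covariates", and its purpose is "to examine associations of MRT dose (number of group sessions attended; number of steps completed) with patient outcomes at the follow-ups". The team then adds that "we will explore whether completion of 12 sessions is as effective as a full dose (24 sessions"). No margin, follow-up visit, outcome, exposure window or named confounder is attached to this analysis.

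Section 5.1 supplies the background. It defines the full dose: "A full dose of MRT is 24 sessions over 12 weeks". It sets 12 sessions as the study minimum and links exposure to residence: "Thus, the majority of patients will have full exposure to the 12-week intervention by virtue of staying in the MH RRTP". Patients who leave early may finish as outpatients, and no end date is given. The reason for the analysis is stated as "To maximize clinical usefulness of the data, we will also examine outcomes as a function of dose".

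The contamination-adjusted analysis in section 5.6 concerns usual-care patients who may have received MRT content. It does not deal with dose inside the MRT arm.

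**The concern.** There are three separate difficulties.

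1. **The question and the method do not match.** Asking whether a smaller dose works as well as a larger one is an equivalence or non-inferiority question. A regression coefficient tested against zero does not answer it, because a wide interval around zero is compatible with a real loss.
2. **Attendance is not randomised.** It depends on how long a patient stays in the residential programme, which brings more usual care as well as more MRT, and on motivation and stability. The only covariate examples nearby, given for the mediation models, are baseline values.
3. **The timing of exposure is open.** Total sessions can include outpatient sessions attended after the 6-month assessment. Some outcomes also look back over the treatment period, so an event that ends attendance can be counted in the outcome as well.

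At stake is how the dose statement in the trial report is read. It could show no difference because the comparison is imprecise, or an advantage for 24 sessions because stable patients stay longer. Neither would be an effect of dose.

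**Working it through.** **Plan's own figures.** The plan gives no figure for the dose analysis. From the power analysis in section 5.6: 365 recruited × 0.80 = 292 followed, and 292 / 2 = 146 per arm. The sizing effect is f² = .02. For two equal groups d = 2√f², so d = 2√.02 = 0.283. The expected effect is f² = .15, so d = 2√.15 = 0.775.

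**Assumed split.** Attendance is not forecast. Suppose 40% of the 146 reach 24 sessions and 30% stop at 12-23: 0.40 × 146 ≈ 58 and 0.30 × 146 ≈ 44.

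**Precision, in SD units.** SE = √(1/58 + 1/44) = 0.200, and the 95% half-width is 1.96 × 0.200 = 0.39. Adjusting for a baseline value that correlates r with the outcome multiplies the SE by √(1 − r²):

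| Assumed r | SE | 95% half-width | Non-significant if true loss is 0.283 |
|---|---|---|---|
| none | 0.200 | 0.39 | 71% |
| 0.5 | 0.173 | 0.34 | 63% |
| 0.7 | 0.143 | 0.28 | 49% |

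The last column is Φ(1.96 − 0.283/SE). Unadjusted, Φ(1.96 − 1.415) = Φ(0.545) = 0.71.

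**Other splits, unadjusted.** With 50%/30% (73 v 44) the figure is 68%. With 30%/40% (44 v 58) it is 71%. With 60%/20% (88 v 29) it is 74%.

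**Larger losses, 58 v 44, unadjusted.** At 0.775 SD, Φ(1.96 − 3.87) = 0.03. At half of that, 0.387 SD, it is 0.51.

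**What a margin-based reading would need.** Take an illustrative margin of 0.28 SD, a true difference of zero, one-sided .025 and 80% power. Then n per group = 2 × (1.96 + 0.842)² / 0.28² ≈ 201 unadjusted, against about 146 in the whole arm. With 58 v 44, the chance of excluding a loss of 0.28 SD is about Φ(0.283/0.200 − 1.96) = 29% unadjusted. An honest reading may well be inconclusive.

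**Selection alone.** Suppose dose has no effect, and an unmeasured stability factor correlates a with attendance and b with outcome. On a normal scale the top 40% of attendance averages 0.966 and the next 30% averages −0.129, a gap of 1.095. The spurious difference is a × b × 1.095:
- a = .3, b = .3: 0.10 SD
- a = .5, b = .3: 0.16 SD
- a = .5, b = .4: 0.22 SD

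If stable patients attend more, this appears as an advantage for 24 sessions. If patients with worse prognosis attend more, the sign reverses, and a true advantage of 0.28 SD would show as 0.28 − 0.10 = 0.18 down to 0.28 − 0.22 = 0.06 SD. These figures are unadjusted, so for the assumed correlations they are upper values.

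**Timing, by outcome.** MRT starts within a week of admission and is scheduled for 12 weeks, so scheduled sessions end around week 13, well before the 6-month visit. PICTS GCT is re-administered at the visit and the ASI composites cover the past 30 days, so neither overlaps scheduled treatment. The ASI recidivism items run from the prior assessment. The TLFB covers 6 months at baseline, and the same look-back at the 6-month visit would span treatment. For these interval outcomes, a relapse or arrest that stops attendance also enters the outcome.

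**The case against.** The wording is modest: the plan speaks of exploring and of associations. The dose question belongs to none of hypotheses 1a-1c and has no part in the power analysis. A reader might infer that the trial will decide whether to halve the dose. The documents do not support that: no section ties any change in delivery to this result, and the stated aim is only clinical usefulness. That objection stands and limits the weight of the point.

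The size also depends on the benchmark. The team expects f² = .15 and used .02 because moderation analyses were planned. Losing the whole expected effect would be missed only about 3% of the time. So it would be wrong to say that a null is the expected result whether or not dose matters; that holds for small dose effects. Baseline adjustment, if applied here, lowers the 71%, and a regression on session count uses the whole arm, which the two-group contrast does not. The extra precision of a linear slope, however, rests on assuming equal benefit per session, which largely presumes the answer to the 12-versus-24 question.

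The timing problem is confined to interval outcomes and to outpatient sessions after an assessment, and nothing shows that such sessions would be common. Outpatient completion also partly separates dose from stay.

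Finally, simply adding length of stay as a covariate could do harm. Completion of the residential programme is a hypothesised mediator under 1c, so adjustment may remove part of the effect sought. That objection is accepted and shapes the fix.

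What survives is that an exploratory label supplies neither a margin nor an exposure window.

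**Conclusion.** The concern holds for a secondary exploratory analysis. As written, a non-significant 12-versus-24 difference cannot support a statement of equal effectiveness. With about 146 MRT patients followed and an assumed 58 v 44 split, a loss of 0.28 SD would go undetected about 50-70% of the time, depending on baseline adjustment (assumed r of 0.7 down to none). Losses near 0.77 SD would rarely be missed.

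The association can also be biased in either direction, by roughly 0.10-0.22 SD before adjustment under the correlations assumed. For interval outcomes the exposure and the outcome can share the same event. The splits, baseline correlations and selection strengths are assumptions, because the documents give none.

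The randomised comparison of MRT with usual care is unaffected, and no view is taken on which dose is right.

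**What to change.** Amend the dose paragraph in section 5.6 as follows.

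- **Exposure window.** Count only sessions and steps completed in a fixed window before the outcome, and never any after the assessment being modelled. For interval outcomes, analyse only time after that window closes.
- **Length of stay.** Show the relation between outcome and length of stay in the usual-care arm as a benchmark; length of stay is already being extracted. Present any model adjusted for it in the MRT arm as a sensitivity analysis only, because programme completion is a hypothesised mediator.
- **Estimate and reading.** Adjust for the baseline value of the outcome. Report the 12-versus-24 difference with its 95% confidence interval against a margin fixed beforehand. State that a non-significant difference will not be reported as equal effectiveness, and label the result an observational association within the MRT arm.

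The cost is plan wording and a little more programming on data already due to be collected. The dose conclusion becomes more modest and may be inconclusive. Outpatient sessions after the window will not count. The window removes the overlap with the outcome but not the selection, and the usual-care benchmark is only rough if MRT itself changes who stays.
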